### 15.5 Appendix 5 – mRS

The modified Rankin Scale (mRS) is an ordinal hierarchical scale ranging from 0 to 5, with higher scores indicating more severe disability. A score of 6 has been added to signify death.

0. No symptoms.
1. No significant disability. Able to carry out all usual activities despite some symptoms.
2. Slight disability. Able to look after own affairs without assistance, but unable to carry out all previous activities.
3. Moderate disability. Requires some help, but able to walk unassisted.
4. Moderately severe disability. Unable to attend to own body needs without assistance and unable to walk unassisted.
5. Severe disability. Requires constant nursing care and attention, bedridden, incontinent.
6. Dead.

## 15.6 Appendix 6 – BI

The Barthel Index (BI) is an ordinal scale used to measure performance in 10 activities of daily living (ADL). Test scores range from 0 to 100, with higher scores indicating better performance in these activities.

### **FEEDING**

0 = unable

5 = needs help cutting, spreading butter, etc., or requires modified diet

10 = independent

### **BATHING**

0 = dependent

5 = independent (or in shower)

### **GROOMING**

0 = needs to help with personal care

5 = independent face/hair/teeth/shaving (implements provided)

### **DRESSING**

0 = dependent

5 = needs help but can do about half unaided

10 = independent (including buttons, zips, laces, etc.)

### **BOWELS**

0 = incontinent (or needs to be given enemas)

5 = occasional accident

10 = continent

### **BLADDER**

0 = incontinent, or catheterized and unable to manage alone

5 = occasional accident

10 = continent

### **TOILET USE**

0 = dependent

5 = needs some help, but can do something alone

10 = independent (on and off, dressing, wiping)

### **TRANSFERS (BED TO CHAIR AND BACK)**

0 = unable, no sitting balance

5 = major help (one or two people, physical), can sit

10 = minor help (verbal or physical)

15 = independent

**MOBILITY (ON LEVEL SURFACES)**

0 = immobile or < 50 yards

5 = wheelchair independent, including corners, > 50 yards

10 = walks with help of one person (verbal or physical) > 50 yards

15 = independent (but may use any aid; for example, stick) > 50 yards

**STAIRS**

0 = unable

5 = needs help (verbal, physical, carrying aid)

10 = independent

**Guidelines**

1. The index should be used as a record of what a patient does, not as a record of what a patient could do.
2. The main aim is to establish degree of independence from any help, physical or verbal, however minor and for whatever reason.
3. The need for supervision renders the patient not independent.
4. A patient's performance should be established using the best available evidence. Asking the patient, friends/relatives and nurses are the usual sources, but direct observation and common sense are also important. However direct testing is not needed.
5. Usually the patient's performance over the preceding 24-48 hours is important, but occasionally longer periods will be relevant.
6. Middle categories imply that the patient supplies over 50 per cent of the effort.
7. Use of aids to be independent is allowed.

### 15.7 Appendix 7 – EuroQoL

The EuroQoL 5-dimensions 5-level (EQ-5D-5L) questionnaire is a standardised measure of health outcome that has been used extensively in patients with stroke.

Under each heading, please tick the ONE box that best describes your health TODAY.

#### MOBILITY

- I have no problems in walking about
- I have slight problems in walking about
- I have moderate problems in walking about
- I have severe problems in walking about
- I am unable to walk about

#### SELF-CARE

- I have no problems washing or dressing myself
- I have slight problems washing or dressing myself
- I have moderate problems washing or dressing myself
- I have severe problems washing or dressing myself
- I am unable to wash or dress myself

#### USUAL ACTIVITIES *(e.g. work, study, housework, family or leisure activities)*

- I have no problems doing my usual activities
- I have slight problems doing my usual activities
- I have moderate problems doing my usual activities
- I have severe problems doing my usual activities
- I am unable to do my usual activities

#### PAIN / DISCOMFORT

- I have no pain or discomfort
- I have slight pain or discomfort
- I have moderate pain or discomfort
- I have severe pain or discomfort
- I have extreme pain or discomfort

#### ANXIETY / DEPRESSION

- I am not anxious or depressed
- I am slightly anxious or depressed
- I am moderately anxious or depressed
- I am severely anxious or depressed

I am extremely anxious or depressed

### 15.8 Appendix 8 – Known side effects of GTN

Very common (>10% of patients): Headache. Nausea, vomiting.

Common (1-10% of patients): Hypotension and/or light-headedness on standing. These symptoms may be associated with dizziness, drowsiness, reflex tachycardia, and a feeling of weakness.

Infrequently (less than 1% of patients): Flushing and allergic skin reaction (e.g. rash), which may be severe. Exfoliative dermatitis has been reported.

Uncommonly collapse may occur (sometimes accompanied by bradyarrhythmia and syncope). Uncommonly severe hypotension may lead to enhanced angina symptoms. A few reports of heartburn, most likely due to a nitrate-induced sphincter relaxation, have been recorded.

Allergic skin reactions to GTN and ingredients (>0.1% but <1%). Slight itching or burning at the site of application. Slight reddening usually disappears without therapeutic measures after the patch has been removed. Allergic contact dermatitis and application site erythema, pruritus, burning, irritation are uncommon.

Unknown frequency: Cardiac disorders like palpitation and disorders related to skin and subcutaneous tissue like generalized rash. Heart rate increase. During the treatment with these patches, a temporary hypoxaemia may occur due to a relative redistribution of the blood flow in hypoventilated alveolar areas. Particularly in patients with coronary artery disease this may lead to a myocardial hypoxia.

Other: Upon removal of the patch, any slight reddening of the skin will usually disappear within a few hours. The application site should be changed regularly to prevent local irritation.

## 15.9 Appendix 9 – Common (potentially) serious complications after stroke

Based on: 

### **Cardiac**

Angina

Arrhythmia

Atrial fibrillation

Angina pectoris

Bradycardia

Cardiac arrest

Cardiomyopathy

Heart failure

Myocardial infarction

Tachycardia

### **Central nervous system**

Brain oedema

Cerebral herniation

Cerebellar herniation

Delirium

Depression

Epileptic seizure

Haemorrhagic transformation of the infarct

Headache

Haematoma expansion

Hydrocephalus

Intraventricular extension of haemorrhage

Increased intracranial pressure

Progressive stroke / Stroke in evolution

Recurrent ischaemic stroke

Recurrent intracerebral haemorrhage

Recurrent stroke

Retinal ischaemia

Sleep disorder

Status epilepticus

Transient ischaemic attack

Transient monocular blindness

### **Gastro-intestinal**

Constipation

Dysphagia

Faecal incontinence

Gastro-intestinal haemorrhage

Ileus

Melena

Mucosal irritation

Nausea

Rectal haemorrhage

Stress ulcer

Vomiting

### **General / other**

Anaemia

Arterial hypertension

Arterial hypotension

Deep vein thrombosis

Dehydration

Fall (and consequences)

Fatigue

Fever

Haematuria

Hip fracture

Hyperglycaemia

Infections

Pain

Pressure sore

Renal failure

Sepsis

[figure not shown]
Syncope

Undernutrition  
Urinary incontinence  
Urinary tract infection

### **Pulmonary**

Aspiration  
Bronchitis  
Central periodic breathing  
Chronic obstructive pulmonary disease  
Dyspnoea  
Obstructive sleep apnoea  
Oxygen desaturation  
Pneumonia  
Pulmonary embolism  
Pulmonary oedema  
Respiratory failure / arrest  
Respiratory tract infection

15.10 Appendix 10 – Flowchart of deferred consent procedure

**Figure 5:** Flowchart of deferred consent procedure specific for the MR ASAP trial. Based on the flowchart proxy-deferred consent in emergency critical care research, by T. Jansen, E. Kompanje, et al.

Glossary: MR ASAP: Multicentre Randomised trial of Acute Stroke treatment in the Ambulance with a nitroglycerin Patch; GTN: glyceryl trinitrate

## 15.11 Trial organisation

The MR ASAP trial is embedded in the CONTRAST consortium. It has an independent leadership, which reports progress in form of milestones to the CONTRAST Scientific committee. Funding is provided through the CONTRAST Consortium based on these milestones.

The Steering committee of the trial consists of all local Principal Investigators (PI) of the participating centers. Each participating center has two PIs: a vascular neurologist and a neuro-interventionist. The Steering committee will meet at least annually. Final decisions concerning protocol changes, publication and reporting will be made by the Steering committee. The Steering committee is chaired by the central PIs of the trial. Decisions will be made in consensus, but if unavoidable by majority vote. Day to day conduct of the trial will be managed by the trial coordinators, who will be supervised by the central PIs of the trial. The Executive committee of the trial consists of the central PIs of the trial and a representation of local PIs. They meet regularly, discuss trial progress and prepare information for the Steering committee.

The Writing committee consists of the Executive committee and local PIs of the five collaborating centers that have contributed the most patients to the trial in the first two years of trial execution. The task of the Writing committee is to prepare the main publication which will be drafted by the study coordinators, supervised by the two central PIs. Typically, the main paper will be authored by the study coordinators (first), the local PIs, the committee members, and the central PIs. Authorship has to comply with the criteria of the International Committee of Medical Journal Editors (ICMJE), <http://www.icmje.org/recommendations/browse/roles-and-responsibilities/defining-the-role-of-authors-and-contributors.html>.

The other trial committees are not trial specific and will be formed in collaboration with the four CONTRAST randomised clinical trials: MR ASAP, MR CLEAN-LATE, MR CLEAN-MED and MR CLEAN-NO IV. These are: the Outcome assessment committee, the Imaging committee, and the Adverse event committee. The committees work for and report to the other three CONTRAST trials.

The Outcome assessment committee consists of at least 3 members, all seasoned neurologists, their task is to evaluate all coded and masked structured reports of outcome assessments at three months of patients in the trials. In this way, the blind assessment is maintained. The chair of this committee will not assess reports, as he is involved as PI in one of the trials.

The Imaging committee is chaired by the CONTRAST WP leaders and consists of neuroradiologists from the collaborating centers. Their task is to assess and evaluate masked baseline and follow-up imaging, which is made per protocol and stored in a central web-based database. Assessments will be stored in Research forms and entered in the clinical database. And will be accessible to investigators after approval by the Steering committee.

The Adverse event committee consists of at least 3 members, including a neurologist and a neuro-interventionist. Their task is to oversee the review and reporting process of all reported serious adverse events. The chair of this committee will not assess reports, as he is involved as PI in one of the trials. The committee will regularly report to the four Steering committees.

15.12      **Appendix 12 – Deferred consent in acute stroke trials**

## Background and rationale

The informed consent procedure is considered fundamental for inclusion in a randomised clinical trial. However, the informed consent procedure in acute stroke research is challenging.

Acute stroke patients are often incapacitated and not able to provide their own consent prior to enrolment. Many patients have a decreased decision making capacity due to severe neurological deficits. In a Dutch registry with data of all patients who underwent endovascular treatment for acute ischemic stroke, 88% had neurological symptoms (aphasia, neglect, lowered consciousness level or confusion) interfering with their capacity to decide about participation in a clinical trial (unpublished data).

According to the 'time is brain' principle and time to treatment effects of endovascular treatment and intravenous thrombolysis, treatment should be initiated as soon as possible.(1) Each hour delay to reperfusion is associated with an increase in absolute risk of death or disability of 6-7%.(2)

As an alternative, a legal representative can be asked to give consent for participation in the trial. However, family members are often not available in the acute setting.(4,5) They might be too overwhelmed to understand the provided information to give valid consent, and experience psychological stress.(6) Also, not all patients want their family members to be their surrogate and many proxies do not know what the patient's wishes are for acute medical research.(7,8,9)

A person who gives consent should be able to understand information, balance benefits and risks and comprehend the severity of the illness. The capacity to consent for enrolment in a trial is subjectively estimated by the researcher or clinician. The comprehension of stroke patients and their proxies of the methods of the trial after providing (prospective) consent is diminished, as shown in a few studies.(10–13) Moreover, data is lacking on whether acute stroke patients and their proxies judge themselves capable of consenting to a clinical trial.

## Deferred consent

An alternative for prospective (proxy) informed consent is deferred consent. In this procedure, consent is asked after enrolment in the study. In the Netherlands, deferred consent is possible in emergency situations. According to the Medical Research Human Subjects Act (Dutch: WMO), procedures of the clinical trial may be undertaken without consent as long as circumstances prevent the giving of consent and if inclusion in the trial may benefit the person in urgent need of medical treatment. No data on deferred consent in acute stroke research has been published yet.

The COllaboration for New Treatment of Acute Stroke (CONTRAST) investigates novel treatment strategies, aimed at preservation of ischemic tissue and improvement of functional outcome in patients with acute ischemic stroke. The CONTRAST consortium entails three trials on endovascular treatment and one prehospital trial. In these trials we will use a deferred consent procedure (figure 1).

## Benefits and drawbacks of deferred consent

- Effect on treatment delays.

The use of the deferred consent procedure might reduce time to study (drug) treatment,

with potential beneficial effects, and reduce delay to standard stroke treatments since the CONTRAST trials will study adaptations of endovascular treatment. No disadvantages of deferred consent on treatment delays are expected.

- Influence on decision-making competence.

Decision-making competence is based on factual understanding, evidencing a choice (consent or refusal), and reasoning and appreciation of the situation. In the acute phase of an emergency situation, patients and relatives are in emotional distress and can be considered temporarily incompetent in these three points. Hence, patients and their relatives can be regarded temporarily incompetent for valid proxy consent in an emergency situation. Deferment of the conversation might lead to a more ethically valid informed consent and a better informed decision.

Still, there is no consistency in the duration of the acute phase of the emergency situation. The moment patients and proxies regain decision-making competence is not defined. Also, patients and proxies might not regard themselves competent of making a decision in the day(s) after the emergency situation.

In addition, some patients and proxies will feel capable of making a decision and could object to the deferred consent procedure itself because they not understand the reasons for the postponement of asking consent. This could interfere with the decision they will make.

- Patient enrolment and selection bias.

It might increase patient enrolment and reduce selection bias resulting in better generalizable study results. Meanwhile, should many patients and proxies object against enrolment, this could likewise contribute to selection bias.

**Main objective**

The aim of the current study is to increase knowledge about the deferred consent procedure in acute stroke research. We will collect and analyse data on logistics of the procedure and on patient recall, satisfaction, and comprehension at three months from randomization.

**Specific objectives**

1. To estimate the proportions of patients and proxies that give consent for and object against enrolment in acute stroke trials using deferred consent procedures;
2. To map the workflow and timeline of the deferred consent procedure;
3. To explore the personal feeling of capability of patients and proxies to provide consent for participation in an acute stroke controlled trial;
4. To explore appreciation of patients and proxies of the deferred informed consent procedure;
5. To investigate recall and comprehension by patients and proxies of study methods of the acute stroke trial for which they provided deferred consent;
6. To compare the observations on 1-5 with data from previous acute stroke trials.

## Methods

### Study design

This study will be a descriptive, observational substudy nested in 4 acute stroke trials within the CONTRAST consortium. We will prospectively collect data on logistics of the deferred consent procedure and ask patients and proxies to fill out questionnaires.

### Study population

Patients and their proxies participating in one or two of the CONTRAST trials.

### Inclusion criteria

- Participation in at least one of the CONTRAST trials.
  - Multicentre Randomised trial of Acute Stroke treatment in the Ambulance with a nitroglycerin Patch (MR ASAP)
  - Multicenter Randomized CLinical trial of Endovascular treatment for Acute ischemic stroke in the Netherlands. The effect of concomitant MEDication: heparin, antiplatelet agents, both or neither (MR CLEAN-MED)
  - Intravenous treatment followed by intra-arterial treatment versus direct intra-arterial treatment for acute ischemic stroke caused by a proximal intracranial occlusion. (MR CLEAN-NO IV)
  - Multicenter Randomized Clinical Trial of Endovascular Stroke treatment in The Netherlands for Late arrivals: MR CLEAN-Late (MR CLEAN-LATE)

### Exclusion criteria

Proxies of deceased patients will not be interviewed.

### Duration of data collection

We aim to collect data on deferred consent of 300 patients during the first year of enrolment in the CONTRAST trials. Data collection will start 3 months after the first inclusion in the study.

**Patient recruitment**Patients / proxies who provided consent for participation in the trial

During the 3 month telephone follow-up of the CONTRAST trial, the subject who provided consent will be asked to participate in this substudy. The purpose of the study will be explained and the study procedures will be described. Questionnaire 1 will be sent to their home address. The feeling of capability for giving consent, appreciation of the informed consent process and recall and comprehension will be explored in this questionnaire. For participation in this substudy, no additional written informed consent from individual subjects is needed.

Patients / proxies who withheld consent for participation in the trial

The patient or proxy who refused to give deferred consent for participation in the CONTRAST trial will be approached. The purpose of the study will be explained and the study procedures will be described. They will be asked to only fill out Questionnaire 2, which concerns the reasons for not giving consent. It will be emphasized that it is not mandatory to answer. No additional questionnaires or interviews will be carried out within this patient group.

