### **8.6 Follow-up of subjects withdrawn from treatment**

In patients who discontinue their allocated treatment, this event will be recorded, including the reason for discontinuation if available. Further treatment will be at the discretion of the treating physician. Follow-up will be carried out as planned.

Due to the deferred consent procedure, study medication has been administered to patients randomised to GTN before informed consent has been obtained. Therefore it is not ethical, for the safety of all patients in the study, to eliminate all information of patients who do not provide informed consent in case of a serious adverse event in the first 7 days, or death during the full study period (both important safety variables for the study). Eliminating these records could result in an underestimation of the true risk of the study treatment and reduce the validity of the data and could lead to major safety concerns for all patients in case patients with a poor outcome will selectively withdraw from study participation. To overcome this safety concern, we will register for non-consenting patients only the variables: patient's study number, date of randomisation, study treatment, final diagnosis, investigator reported serious adverse events in the first 7 days (or until hospital discharge, if earlier), in-hospital mortality (yes/no). All other information will completely be erased from the patient's study record. The link to the study database will be erased from the medical record.

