### 1. Patient enrolment

The CONTRAST trials use different deferred informed consent forms (ICFs):

- 1) Patient: the patient is mentally competent to provide consent, as estimated by the researcher/clinician
  
- 2) Proxy (partner or family member): the patient is not mentally competent to provide consent, as estimated by the researcher/clinician, and the researcher/clinician believes it is ethically valid to inform and ask for consent

In case the patient has deceased before consent could be asked, the data which has been documented so far may be used in an anonymous fashion for study purposes and the proxy will be informed (figure 1).

The following data will be documented regarding patient enrolment:

- the number of patients providing consent vs. not providing consent + reasons for not providing consent
  
- the number of proxies providing consent vs. not providing consent + reasons for not providing consent
  
- the number of patients who deceased before consent could be asked
  
- the number of patients that withdrew their consent within 3 months

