**Nature and extent of the burden of participation**

The study procedures will require an estimated maximum of 30 minutes of the subject's time at 3 months (Questionnaire 1) and 5 minutes of the subject's time during hospital admission (Questionnaire 2) and. We therefore consider the burden minimal.

[figure not shown]

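### Deferred-consent substudy: a month-3 start for all data collection means that patients or proxies who refuse in the first 3 months are not offered Questionnaire 2

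*Protocol*

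**What the plan says.** All references are to the protocol; the substudy is described in Appendix 12 (section 15.12).

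- **Target and start.** Under Duration of data collection: "We aim to collect data on deferred consent of 300 patients during the first year of enrolment in the CONTRAST trials". The next sentence sets the start: "Data collection will start 3 months after the first inclusion in the study". It makes no exception for any instrument.
- **Consenters (Questionnaire 1).** "During the 3 month telephone follow-up of the CONTRAST trial, the subject who provided consent will be asked to participate in this substudy". The questionnaire is then posted to them.
- **Refusers (Questionnaire 2).** "The patient or proxy who refused to give deferred consent for participation in the CONTRAST trial will be approached". That text gives no time. The burden section does: it counts "5 minutes of the subject's time during hospital admission (Questionnaire 2").
- **Objective and enrolment data.** The first specific objective is "To estimate the proportions of patients and proxies that give consent for and object against enrolment". The section 1. Patient enrolment lists, as data to be documented, "the number of patients providing consent vs. not providing consent + reasons for not providing consent", and the same for proxies. The list is separate from Questionnaire 2 and has no start date of its own.
- **What the main trial keeps.** Section 8.4 notes study number, allocation and refusal even for patients who allow no other use of their data. Section 11.2 puts the refusal, and the reason where there is one, in the clinical chart. Section 8.6 retains a short list of safety variables for non-consenters, erases the rest of the study record, and adds: "The link to the study database will be erased from the medical record".

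**The concern.** One start date is applied to two questionnaires whose lags from enrolment differ. Questionnaire 1 comes about 3 months after enrolment, so opening collection at month 3 still reaches back to the first patient. Questionnaire 2 is completed during the admission, so opening at month 3 reaches only those who refuse from then on. Consenters from months 0 to 3 are asked for their views; refusers from the same months are not.

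What is at stake is limited but real. Questionnaire 2 offers fixed answers, such as too much information, poor understanding of the explanation, or being asked too soon after the stroke. It also records education and, for proxies, sex and age. The substudy's Baseline information section documents education only for the person who gave consent, so Questionnaire 2 is the only stated source of it for refusers. The Handling of data and documents section says that the substudy's conclusions may change the consent procedure while the trials are still enrolling. The first months, when sites are newest to the procedure, are where that feedback is likely to be most useful.

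**Working it through.** The plan gives no sample-size or precision figure to reproduce; the 300 is a target without a derivation. The check is therefore a comparison of enrolment windows.

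**Inputs from the protocol**
- Collection opens at month 3 after the first inclusion (Appendix 12, Duration of data collection).
- The reference period is the first year, months 0 to 12 (same place).
- Lag to Questionnaire 1 is about 3 months. The main trial's 90-day visit has a 14-day tolerance either way (section 8.1.1), so 76 to 104 days, or 2.5 to 3.4 months.
- Lag to Questionnaire 2 is about 0 months. Consent is sought within 24 hours according to Appendix 12 (workflow section), and in any case within the admission according to section 11.2.

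**Assumption.** The protocol gives no accrual pattern. Flat accrual and a linear ramp from zero are used to show a range.

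**Step 1: earliest enrolment month reached** = opening month minus lag.
- Questionnaire 1: 3 − 3 = month 0.
- Questionnaire 2: 3 − 0 = month 3.

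**Step 2: enrolment windows under two readings of the first year**

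| Reading | Questionnaire 1 | Questionnaire 2 | Overlap |
|---|---|---|---|
| The year bounds data collection | months 0–9 | months 3–12 | 6 of 9 months |
| The year bounds enrolment (Questionnaire 1 runs to month 15) | months 0–12 | months 3–12 | 9 of 12 months |

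The windows are offset by 3 months at the start under both readings, but they mostly overlap.

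**Step 3: share of first-year refusers not offered Questionnaire 2** = accrual in months 0–3 divided by accrual in months 0–12, with a constant refusal rate.
- Flat accrual: 3/12 = 25%.
- Linear ramp: 3²/12² = 9/144 = 6.25%, about 6%.

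**Step 4: in numbers.** Suppose that the 300 are the people asked for consent and that 5% to 20% refuse (both assumed; the protocol gives no refusal rate).
- At 5%: 300 × 0.05 = 15 refusers. Missed: 15 × 0.25 = 3.75 (flat) or 15 × 0.0625 = 0.94 (ramp).
- At 20%: 300 × 0.20 = 60 refusers. Missed: 60 × 0.25 = 15 (flat) or 60 × 0.0625 = 3.75 (ramp).

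That is about 1 to 4 questionnaires under the ramp and about 4 to 15 under flat accrual.

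**The case against.** The best reply is that the start sentence was meant for Questionnaire 1 only. Other substudy data cannot sensibly wait until month 3: the times of the consent conversation and signature are written on the consent form when they occur, and the baseline data are already collected by the trials. On that view this is loose wording, not a decision to skip early refusers. That may well be the intention, but the text does not say so. No section gives Questionnaire 2 an earlier start or a retrospective approach, and a site following the sentence would not hand it out.

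A second reply is that the main trial already holds the information. For counts this stands: refusal is noted for each patient, so the consent and objection proportions can be obtained from the first inclusion. For reasons it stands in part. The chart holds a reason if one is available, but the minimum sets in sections 8.4 and 8.6 do not include it, and the chart does not give the structured answers or the education level.

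A third reply is that little depends on this. The planned analysis is descriptive, its named comparison is with an earlier Dutch thrombectomy trial, and Questionnaire 2 is voluntary. This also stands, and it sets the weight of the point.

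**Conclusion.** The point holds in a narrow form. As written, those who refuse in the first 3 months are not offered Questionnaire 2, although consenters from those months receive Questionnaire 1. The loss is about 6% to 25% of first-year refusers, depending on the assumed accrual, and it concerns structured reasons and education level only. The figures treat refusal as occurring close to enrolment and the refusal rate as constant. They also take a single clock, although the substudy spans four trials and does not say which trial's first inclusion counts. The trial's primary analysis is not involved.

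A reader might infer more than the protocol supports:

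- **That the consent and refusal proportions are biased.** If a refusal rate were built from questionnaire coverage under the linear ramp, Questionnaire 1 would cover 81/144 = 56% of first-year enrolment and Questionnaire 2 135/144 = 94%. A true 5% would then appear as 0.05 × 0.9375 / (0.05 × 0.9375 + 0.95 × 0.5625) = 8.1%. No section plans that calculation. The proportions rest on the enrolment counts, and under flat accrual the coverages are equal and the distortion disappears. The 25% above needs flat accrual, so the two figures cannot be used together.
- **That no reasons for early refusals will exist.** Section 11.2 and the Patient enrolment list provide for reasons where available.
- **That early refusers cannot be approached later.** Section 8.6 removes the link to the study database from the medical record, but the refusal itself stays in the chart. The protocol neither plans a later approach nor rules one out.
- **That consenters and refusers form non-comparable cohorts.** Their windows overlap for most of the year, the two questionnaires ask different things, and no comparison of their answers is planned.

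**What to change.** In Appendix 12, Duration of data collection, replace the single start by three statements:

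1. Questionnaire 2 and the consent/refusal log start with the first inclusion.
2. Questionnaire 1 starts at the first 3-month follow-up.
3. The substudy cohort is defined by enrolment date, and each consenter receives Questionnaire 1 on reaching 3 months, even if that falls after month 12.

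Both questionnaires then draw on the same enrolment period, and no first-year refuser is missed because of the start date. It would help to say in the same place which trial's first inclusion is meant, or that each trial has its own clock.

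The cost is a few lines of text. Questionnaire 2 already exists, is voluntary, and takes an estimated 5 minutes. The small downside is that Questionnaire 1 returns run about 3 months past the first year (12 + 3 = month 15). The change has to be in place before the first inclusion to have its full effect, because answers not collected during an early admission cannot be collected in that setting later.
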